**Table: Sample Sizes under Various Assumptions**

Proportion of infants in each dosing group	45%/45%	45%/45%	40%/50%	40%/50%	35%/55%	35%/55%
Event rates	80% power	90% power	80% power	90% power	80% power	90% power
60% vs 45%	1014	1352	1140	1520	1303	1738
60% vs 40%	563	753	634	847	724	968

## b. Inclusion/Exclusion Criteria

### Inclusion Criteria:

- Gestational age of  $36^{+6}$  weeks or less
- Treated with surfactant
- Record of birth-weight available
- Infants born after the initiation date of the study
- Parental opt-out consent

### Exclusion Criteria:

- Gestational age of  $37^{+0}$  weeks and above

## 5. Data and Research Management

Selected study sites for participation will be approached to allow healthcare professional the opportunity to discuss the study and its aims. Data champions will be appointed at each study site; their responsibility will be to ensure data are fully recorded on all eligible infants who have provided opt-out consent.

Confirmation of quality assurance will be obtained from the NNRD every 3 months. No patient identifiers, or individual Trust identifiers, will be included in this study file.

Interim anonymised data will be analysed by an independent statistician within 3 months of the last patient recruited reaching 28 days post birth. All data will be anonymised and shall include no individual patient data.

The final anonymised data will be analysed by an independent statistician within 3 months of completion of the study (when the last patient has reached the 2 year time point). All data will be anonymised and shall include no individual patient data.

Once the final analysis of the data has been carried out, the original data will be destroyed. The analysed data will be kept by Chiesi for a minimum period of 5 years to allow dissemination.

This is an observational study, and the NNRD hold the relevant permissions for the data to be provided in anonymised form for the purposes of research by parties other than the NNRD upon specific Research Ethics Committee approval. Opt-out consent will be gained from the parents of babies eligible for inclusion in the study to confirm that they are happy for their baby's data to be utilised for this study.

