**b. Rationale for study**

The rationale for this study is the clinical relevance of understanding whether surfactant dose affects neonatal outcomes in infants with RDS who are treated in the immediate postnatal period.

In a research environment, the dose of surfactant is rigorously controlled, usually administered at a dose of 100mg/kg or 200mg/kg. In clinical practice, clinicians more frequently follow the 'whole vial dosing' approach, where a full vial is given aiming to get as close as possible to the desired dose. Reasons for whole vial use include reduction of waste and administration of surfactant shortly after birth where an infant's weight is unknown. It is unclear whether whole vial dosing leads to under-dosing or over-dosing and whether either situation affects outcomes.

Information regarding the dose of surfactant delivered, and the method of administration, are not currently routinely recorded in the UK.

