### 3. Research Design

It is proposed to minimise data collection requirements for this study through incorporation into routine clinical care. The data items required all form part of what would normally be recorded in a patient's case records. Hence it is proposed to obtain these from the Neonatal Network Research Database (NNRD).

The Neonatal Network Research Database (NNRD) is an electronic platform where neonatal patient data on all admissions to a National Health Service (NHS) neonatal unit in England, Scotland or Wales are recorded. Clinical data on all admissions to NHS neonatal units are entered by healthcare professionals, as part of routine clinical practice, onto electronic patient record systems at the point of care; from these data, approximately 450 data items (the Neonatal Data Set, an NHS Information Standard) are extracted quarterly to form the NNRD. Data held in the NNRD are used for audits, research, service evaluations and quality improvement projects.

A small number of additional data items not currently held in the NNRD, are required for this study. They are however all items that would normally be recorded in the patient's case notes; hence it is proposed to incorporate these into the electronic data capture system. Specific Research Ethics Approval will be sought for this study.

Multiple centres across the UK will be selected to participate. The parents of eligible babies will be approached for op-out consent for their child's data to be included in the study.

The study will continue recruiting until 1300 babies have been consented, and will remain open until 2 year follow up data has been obtained for those babies born < 30 weeks gestation. There will be no further follow up in those babies that have no data available at the 2 year follow-up.

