## 6. Data Analysis

The primary objective of the study is to compare the two dosing groups (100-130 mg/kg and 170-200 mg/kg) in terms of the proportions of infants who require mechanical ventilation within four days of birth. This comparison will be undertaken primarily through propensity score matching with the key sensitivity analysis comparing the unmatched dosing groups.

The propensity score model will be a logistic regression model with binary 'outcome' corresponding to dosing group and with the following baseline factors included in the model; birth weight, gestational age, sex, antenatal steroids, inborn, age at first dose, and baseline FiO2. This analysis will be based on the modified Intention-to-Treat population (mITT) defined as all patients who satisfy the inclusion/exclusion criteria, who provide complete data on each of the baseline factors considered for inclusion in the propensity model and who are evaluable for the primary endpoint.

Following 1 to 1 matching between the dosing groups 100-130 mg/kg and 170-200 mg/kg using a caliper of 0.025, an analysis of the matched cohorts will be based on a logistic regression model with the primary endpoint, requiring mechanical ventilation within 4 days of birth, as the response and dosing group plus each of the covariates listed used in the propensity score model included as terms in this analysis model. The key sensitivity analysis will compare the dosing groups in the full mITT population using the same modelling structure.

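### No unit code is planned for the analysis file and no model has a centre term, so this multicentre dose comparison, as written, can neither adjust for unit nor allow for clustering

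*Protocol*

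**What the plan says.** Protocol Section 3 makes the study multicentre: "Multiple centres across the UK will be selected to participate". The number of centres is not given.

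Section 5, among its anonymisation commitments, says: "No patient identifiers, or individual Trust identifiers, will be included in this study file".

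The added data items (Section 3, NNRD Fields), the comparative fields (Section 3a) and Appendix A contain no unit or site code, whether real or pseudonymous.

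Section 6 lists the propensity score covariates as "birth weight, gestational age, sex, antenatal steroids, inborn, age at first dose, and baseline" FiO2. All seven describe the infant or its care. Inborn status is the only one that concerns place of birth, and it does not identify a unit. After 1:1 matching, the outcome model has "dosing group plus each of the covariates listed used in the propensity score model included as terms in this analysis model". The unmatched comparison repeats this: "The key sensitivity analysis will compare the dosing groups in the full mITT population using the same modelling structure". Section 6 names no matching within centre, random effect or robust variance.

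On how dose arises, Section 2b says: "In clinical practice, clinicians more frequently follow the 'whole vial dosing' approach".

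**The concern.** Dose is not randomised, so the primary comparison depends on measuring the common causes of dose and outcome. The primary endpoint is mechanical ventilation within four days of birth, which depends partly on how ready clinicians are to ventilate. If units that tend to give the higher dose also tend to favour non-invasive support, unit is a common cause of exposure and outcome that none of the seven covariates measures. Part of the unit effect would then be read as a dose effect.

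The second issue is variance. Infants treated in one unit may have correlated outcomes. To the extent that dose also follows the unit, an ordinary logistic regression gives standard errors that are too small.

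This is not only a matter of analysis detail. An analysis plan can choose a variance estimator or add a term, but it cannot adjust for or cluster on a variable that the file does not hold.

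**Working it through.** **Step 1. Does the planned sample size allow for clustering?** Inputs from Section 4a: 60% versus 45%, 80% power, two-sided 5%, 25% of the smaller group unmatched.

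- Per arm, unpooled variance: (1.960 + 0.842)² × (0.60 × 0.40 + 0.45 × 0.55) / 0.15² = 170.1, so 171.
- Total N = 2 × 171 / (0.75 × share of the smaller group). Shares of 0.45, 0.40 and 0.35 give 1014, 1140 and 1303.

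These are the Protocol's own figures. They are reached with infants treated as independent (design effect 1), so the table has no allowance for clustering.

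**Step 2. Type I error if clustering is ignored (upper case).** Assumptions not in the Protocol: 30 centres of equal size, dose set entirely by unit, ICC 0.02 to 0.10. Matched infants: 2 × 342 = 684, where 342 is the number of matched infants that the table requires of the smaller group.

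- Infants per centre: m = 684 / 30 = 22.8.
- Design effect: DE = 1 + (m − 1) × ICC.
- True type I error: 2 × (1 − Φ(1.96 / √DE)).
- Correct interval width relative to the naive one: √DE.

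| ICC | DE | True type I error | Interval widening |
|---|---|---|---|
| 0.02 | 1.44 | 10% | 20% |
| 0.05 | 2.09 | 17% | 45% |
| 0.10 | 3.18 | 27% | 78% |

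The result depends on the assumed number of centres. With N = 1300, ICC 0.05 and the range of splits in Section 4a, 20 centres give 23% to 27% and 40 centres give 14% to 17%.

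**Step 3. Confounding by unit (illustration, no true dose effect).** At a 40/50 split, N = 1300 gives 1300 × 0.40 × 0.75 = 390 pairs. Assume two types of unit. The high-ventilation type supplies 70% of the lower-dose infants and 30% of the higher-dose infants. Assume also that the covariates do not capture the unit difference.

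- Spurious difference = unit difference × (0.70 − 0.30).
- Unit difference of 20 points: 0.20 × 0.40 = 8 points, just over half of the planned 15-point effect. The test rejects about 61% of the time.
- Unit difference of 10 points: 0.10 × 0.40 = 4 points. The test rejects about 20% of the time.

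**Step 4. Is lost power the harm?** Mostly not. The formula needs 171 per arm, while the table asks the smaller group for 2 × 171 = 342 matched infants. At N = 1300, with the planned match rate, power under independence is about 98% to 99% across the three splits. A design effect of 2 still leaves about 80% to 89%. The harm is bias and intervals that are too narrow.

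**The case against.** **A reader might infer that the file is stripped of every centre identifier, or that a unit code is forbidden.** The text does not go that far. The sentence in Section 5 excludes individual Trust identifiers for confidentiality. A Trust is not the same as a neonatal unit, and a random code is neither barred nor planned. The field lists are also not a perfect guide: inborn status is needed for the propensity model but appears in none of them, although Section 3a presents Appendix A as the full list. What stands is that no unit code is provided for, and that the specified models would not use one.

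**A reader might infer that dose is set by unit policy.** The Protocol does not say this. Section 2b speaks of clinicians, and describes practice in which "a full vial is given aiming to get as close as possible to the desired dose". Under whole-vial dosing, mg/kg depends on vial size and the infant's weight, so dose would vary within units, and birth weight is already in both models. This weakens the variance argument considerably. It does not remove possible confounding, because the choice of target dose and the threshold for ventilating may still differ between units.

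**A reader might take 10% to 27% as the expected error rate.** The formula holds for an exposure fixed by cluster with equal cluster sizes. The relevant ICC is the one left after covariate adjustment, which is unknown. The figures are an upper case on assumed inputs.

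**A reader might conclude that no later analysis could repair the omission.** That is too strong. The source records sit with the database, Section 9a provides for amendments, and the original study data are destroyed only after the final analysis. It is also fair to say that the choice of variance estimator is commonly left to an analysis plan, which is not at hand. The narrower point survives: without a unit code in the file, that plan has nothing to cluster on.

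**Conclusion.** The point holds in limited form. As written, the Protocol excludes Trust identifiers, requests no pseudonymous unit code and fixes propensity, matched and unmatched models without a centre term. The comparison therefore cannot adjust for unit-level confounding or allow for clustering by unit.

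The size is unknown, because the Protocol gives neither an ICC nor a number of centres, and variation in practice between units is inferred. The upper case in Step 2 puts the type I error of a nominal 5% test at about 10% to 27%. The inflation shrinks as dose varies within units. Confounding could persist even then, and the 4- and 8-point differences in Step 3 show what moderate imbalance would do; they are not estimates.

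The documents do not show that the primary result will be biased. They show that the plan has no means of checking or correcting for it. This is a worthwhile, inexpensive improvement to make before the extract is built.

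**What to change.** 1. Before extraction, ask the database to supply a random, study-specific code for the unit where the first dose was given, with the key held only at the database. Add the field to Section 3a and Appendix A.
2. Reword Section 5 so that it excludes only identifiable Trust names or codes.
3. In Section 6, fit the matched primary model and the unmatched sensitivity analysis with a unit random intercept or unit-clustered standard errors.
4. Report an analysis adjusted for unit as well. Clustered standard errors correct the variance but do nothing about confounding.
5. Keep unit in the propensity model, or matching within unit, as a sensitivity analysis only. With a caliper of 0.025 either could reduce the number of matches, possibly beyond the 25% allowance in Section 4a.

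Cost: one pseudonymous field, a line in the data request and ethics documents, and a small disclosure risk limited by keeping the key at the database. Intervals will be wider where clustering is real, by about 20% to 80% in the upper case above and by less if dose varies within units.

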## 6. Data Analysis

The primary objective of the study is to compare the two dosing groups (100-130 mg/kg and 170-200 mg/kg) in terms of the proportions of infants who require mechanical ventilation within four days of birth. This comparison will be undertaken primarily through propensity score matching with the key sensitivity analysis comparing the unmatched dosing groups.

The propensity score model will be a logistic regression model with binary 'outcome' corresponding to dosing group and with the following baseline factors included in the model; birth weight, gestational age, sex, antenatal steroids, inborn, age at first dose, and baseline FiO2. This analysis will be based on the modified Intention-to-Treat population (mITT) defined as all patients who satisfy the inclusion/exclusion criteria, who provide complete data on each of the baseline factors considered for inclusion in the propensity model and who are evaluable for the primary endpoint.

Following 1 to 1 matching between the dosing groups 100-130 mg/kg and 170-200 mg/kg using a caliper of 0.025, an analysis of the matched cohorts will be based on a logistic regression model with the primary endpoint, requiring mechanical ventilation within 4 days of birth, as the response and dosing group plus each of the covariates listed used in the propensity score model included as terms in this analysis model. The key sensitivity analysis will compare the dosing groups in the full mITT population using the same modelling structure.

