#### *Surfactant dose*

The licensed dose of surfactant for preterm infants with RDS is 100 to 200mg/kg. A dose of 200mg/kg reduces FiO2 requirements and the need for redosing as well as indicating possibility of reduced mortality and oxygen requirement at 36 weeks post menstrual age. A pharmacokinetic study has also demonstrated that a dose of 200mg/kg results in a higher half-life of surfactant compared to the 100mg/kg.

*Administration techniques*

The drive towards minimally invasive treatments for premature infants as well as the difficulties associated with intubation for surfactant delivery has led to innovations in surfactant administration. Minimally invasive surfactant administration (MIST) or less invasive surfactant administration (LISA) are techniques that use a thin catheter (Angiocath or nasogastric tube) to deliver surfactant whilst the infant is spontaneously breathing and this method is gaining popularity across Europe. A recent meta-analysis found that the use of LISA/MIST has reduced the composite outcome of death or bronchopulmonary dysplasia (BDP) at 36 weeks, need for mechanical ventilation within 72 hours of birth, or need for mechanical ventilation anytime during the neonatal intensive care stay.

Use of the LISA/MIST techniques of surfactant administration also supports the drive towards non-invasive methods of ventilatory support, as no intubation is required to instil the surfactant, in contrast to the intubate-surfactant-extubate (INSURE) method.

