## NNRD Fields

Surfactant can be administered prophylactically (usually within the delivery room) or as rescue (usually within the neonatal ward). If surfactant is given prophylactically, it is assumed that this is the first administration.

If administered prophylactically, it is proposed that the following data items are added under the 'NNUEpisodes-Labour & Delivery' category within the electronic record:

	Question	Answer
1	Volume of surfactant administered in millilitres (mL)	[free text box]
2	Method of surfactant administration	
 
• Endotracheal tube
 
• INSURE (endotracheal tube in place for 15 minutes or less)
 
• Thin catheter for minimally invasive/less invasive surfactant administration
 
• Other
 

3	Time of initial surfactant administration	[free text]
4	Specify any analgesics and/or sedatives used for surfactant administration (drug and dose)	[free text]

Surfactant can also be administered in a rescue setting, usually within the neonatal unit. In this setting, the frequency of administration is captured (i.e. whether this is the infant's first, second or third dose). The following fields are proposed under the 'Respiratory-Daily' category:

	Question	Answer
1	Volume of surfactant administered in first dose, millilitres (mL)	[free text box]
2	Specify the method of surfactant administration	
 
• Endotracheal tube
 
• INSURE (endotracheal tube in place for 15 minutes or less)
 
• Thin catheter for minimally invasive/less invasive surfactant administration
 
• Other
 

3	How many doses of surfactant were administered today?	[Free text box]
4	Time of initial surfactant administration	[free text]
5	Specify any analgesics and/or sedatives used for surfactant administration (drug and dose)	[free text]
6	FiO 2 at point of decision to administer surfactant	
 
• < 30 %
 
• 30- 39 %
 
• 40 - 49 %
 
• 50 - 59 %
 
• ≥ 60 %
 

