### a. Comparative fields

In order to investigate whether surfactant dose affects neonatal outcomes, the following data will be obtained from the NNRDs:

	NNRD field	Purpose of using this field for this study
1	Demographics > Birth weight	Using this field alongside the volume of surfactant used, the dose of surfactant will be calculated.
2	Demographics > Sex of the baby (phenotypic)	Characterisation of cohort
3	Demographics > Gestation weeks and day	Inclusion/exclusion criteria
4	Antenatal > Were steroids given during pregnancy?	Characterisation of cohort
5	Antenatal > Number of antenatal steroid courses given	Characterisation of cohort
6	Labour & delivery > Methods of resuscitation	Characterisation of cohort
7	Labour & delivery > Drugs used during resuscitation	Characterisation of cohort
8	Labour & delivery > Was surfactant given during resuscitation?	Characterisation of cohort
9	Respiratory > Respiration: Surfactant given today	Inclusion/exclusion criteria
10	Discharge details > Discharge time and date (anonymised)	Duration of hospitalisation, age at discharge
11	Discharge details > Date of death and time - anonymised	Calculation of mortality
12	Discharge details > cause of death	Determination of outcomes
13	Discharge details > Discharge oxygen	To investigate whether the dose of surfactants can affect whether infants are discharged on oxygen.
14	Respiratory > Respiratory support device and support mode (daily)	To investigate whether using there is a correlation between surfactant dose and respiratory device
16	Discharge details > Clinical diagnoses at discharge	To correlate the dose of surfactant, and/or method of surfactant administration is related to clinical diagnoses at discharge
17	Retinopathy of prematurity > ROP stage*	To determine whether the dose of surfactant is related to the severity of retinopathy of prematurity
18	Cranial ultrasound scan > IVH**	To determine whether the dose of surfactant is related to the severity of periventricular haemorrhage

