## The effect of surfactant dose on outcomes in preterm infants with RDS

NNUEEpisodes	Antenatal (Pregnancy details)	Were steroids given during pregnancy?	Steroids Antenatal Given	STEROIDS GIVEN DURING PREGNANCY TO MATURE FETAL LUNGS INDICATOR	an 1	Derived N No Y Yes 9 Unknown	Administration of any dose of steroid to mother (dexamethasone or betamethasone), at any time during pregnancy, with the intention of maturing foetal lungs.	Used to compare outcomes for babies
NNUEEpisodes	Antenatal (Pregnancy details)	Number of antenatal steroid courses given	Steroids Antenatal Courses	ANTENATAL STEROID COURSE COMPLETION STATUS CODE	n1	1 - Complete: A full course of steroids at any time during pregnancy 2 - Incomplete: At least one injection of steroids given at any time during pregnancy 3 - Not Given 9 - Unknown	A complete course of steroids is defined by the RCOG guideline as two 12mg doses of betamethasone, given intramuscularly, 24 hours apart. Some units may use another regimen, including a different steroid. A complete course is one which complies with the local protocol.	Used to compare outcomes for babies
NNUEEpisodes	Labour & delivery	Methods of resuscitation	Methods OfResuscitation	NEONATAL RESUSCITATION METHOD (NATIONAL NEONATAL DATA SET)	an 3	00 None 10 Stimulation 11 Positioning managing airways 12 Oxygen 13 Suction 14 Bag and face mask IPPV 15 Intubation 16 Cardiac massage	Interventions used during resuscitation or stabilisation immediately after delivery of the baby.	Used to monitor neonatal outcomes

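### The dose comparison adjusts for seven fixed factors that leave out route of first dose and intubation before it, so it can stay confounded, and the key sensitivity analysis cannot show this

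*Protocol*

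**What the plan says.** Protocol section 6 (Data Analysis) makes the primary comparison, 100-130 against 170-200 mg/kg, through 1:1 propensity score matching. The score is a logistic regression "with the following baseline factors included in the model; birth weight, gestational age, sex, antenatal steroids, inborn, age at first dose", and baseline FiO2. The matched cohorts are then analysed by logistic regression with "dosing group plus each of the covariates listed used in the propensity score model included as terms in this analysis model". For the check on this result: "The key sensitivity analysis will compare the dosing groups in the full mITT population using the same modelling structure". One closed list of seven factors therefore governs all three steps.

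The protocol obtains more than these seven:
- Section 3 (NNRD Fields) has an entry for "Method of surfactant administration" in the delivery-room table and an equivalent entry in the rescue table. The options are endotracheal tube, INSURE, thin catheter and other.
- Section 3a (Comparative fields) lists "Methods of resuscitation". Appendix A shows that its codes include intubation ("15 Intubation 16 Cardiac massage").
- Section 2a (Administration techniques) cites a meta-analysis in which thin-catheter techniques reduced the "need for mechanical ventilation within 72 hours of birth".
- Section 2b makes the association between route and ventilation within four days an exploratory objective.

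**The concern.** Dose is not assigned in this study, so the primary result depends on which factors are balanced. By the protocol's own background, route bears on an outcome very close to the primary endpoint. An infant already intubated before surfactant may be on a ventilator whatever dose follows. If either factor is distributed differently between the dosing groups among infants alike on the seven listed factors, matching leaves that difference in place and the outcome model does not remove it.

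The unmatched analysis is no safeguard. It drops the matching but keeps the covariates, so it carries the same omission. Agreement between the two analyses could be read as robustness when both share one bias.

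**Working it through.** **1. The planned effect and sample size.** Inputs from section 4a: 60% against 45%, 80% power, two-sided 5%, and 25% of the smaller group unmatched.

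n per group = (1.96 + 0.8416)² × (0.60×0.40 + 0.45×0.55) / 0.15² = 7.849 × 0.4875 / 0.0225 = 170.1, so 171.

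The protocol's totals follow from 2 × 171 / (0.75 × s), where s is the share of infants in the smaller group:

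| s | Calculation | Total | Protocol |
|---|---|---|---|
| 45% | 342 / 0.3375 | 1014 | 1014 |
| 40% | 342 / 0.30 | 1140 | 1140 |
| 35% | 342 / 0.2625 | 1303 | 1303 |

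The table is reproduced. It draws all 342 infants from the smaller group, whereas 171 pairs would meet the stated power. This is why step 4 finds slack.

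**2. Possible bias.** Suppose dose has no effect. For a binary factor left out of the models:

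spurious difference = (difference in ventilation risk by the factor) × (difference in its prevalence between the matched groups, given the seven factors)

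The protocol gives neither input, so both are assumptions:

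| Effect of factor on ventilation | Imbalance 5 points | 10 | 20 | 30 |
|---|---|---|---|---|
| 10 points | 0.5 | 1 | 2 | 3 |
| 20 points | 1 | 2 | 4 | 6 |
| 30 points | 1.5 | 3 | 6 | 9 |
| 40 points | 2 | 4 | 8 | 12 |

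With no imbalance every entry is zero.

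**3. What a mid-range entry does to the test.** Take 6 points (30 × 0.20), centred on 52.5%, so 55.5% against 49.5%. At a 35%/55% split, 1300 infants give 1300 × 0.35 × 0.75 = 341 pairs.

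SE = √[(0.555×0.445 + 0.495×0.505) / 341] = 0.0382, and 0.06 / 0.0382 = 1.57.

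The chance of a significant result without any dose effect is about 1 − Φ(1.96 − 1.57) = 35%, instead of 5%. With 171 pairs it is about 20%.

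**4. Can the sample bear a richer matching rule?** Suppose 50% of the smaller group goes unmatched instead of 25%. Power for 60% against 45% with n pairs, treating the matched groups as independent, is Φ{[0.15√n − 1.96√(2×0.525×0.475)] / √0.4875}.

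| Smaller group | Pairs | Power |
|---|---|---|
| 45% | 1300 × 0.45 × 0.5 = 292.5 | 95.5% |
| 40% | 1300 × 0.40 × 0.5 = 260 | 93.1% |
| 35% | 1300 × 0.35 × 0.5 = 227.5 | 89.6% |

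**The case against.** **Confounding is not demonstrated.** A factor that precedes dosing and predicts ventilation confounds only if it is also associated with dose group, given the seven factors. Nothing in the protocol links route or resuscitation intubation to dose. The nearest statement, in section 2b, is that whole vials are used partly because surfactant is given soon after birth before weight is known. That concerns setting, and age at first dose already captures part of it. This objection stands. A reader might infer that the comparison is confounded, but the text supports only that it can be.

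**Evidence that a factor drives ventilation exists for route only, and without a size.** This stands. Calling all the omitted factors strong determinants would go beyond the document.

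**Route is not wholly a pre-dose variable.** Section 3 defines INSURE by the tube being in place for 15 minutes or less, which is known only after dosing and may reflect early response. Matching on all four route categories would condition on post-dose information. This stands and changes the fix.

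**Infants ventilated at dosing raise an endpoint problem.** If all of them count as events, 40% of the others are ventilated, and the status is held by 60% and 40% of the two groups, the rates are 0.6 + 0.4×0.4 = 76% and 0.4 + 0.6×0.4 = 64%. This 12-point gap is a constructed case, not an estimate. It also makes that level of the covariate all events, so the outcome model separates and pairs within that level say nothing about dose. A covariate alone does not cure this.

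**Setting may be moot.** FiO2 at the decision to treat is only in the rescue table, and the mITT requires complete baseline factors. Unless FiO2 comes from elsewhere, infants treated prophylactically leave the analysis and setting does not vary.

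**The stated purpose of the resuscitation fields proves nothing.** Section 3a labels them as describing the cohort, but sex and antenatal steroids carry the same label and are in the model. This stands.

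**The analysis plan may add to this.** Balance checks and supplementary analyses can be left to it. The covariate list cannot be treated that way, because the protocol itself fixes it for both the primary and the key sensitivity analysis.

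**Conclusion.** The point holds as a risk of bias built into the stated analyses. Two factors that the protocol collects, one of which its own background ties to early ventilation, are missing from the propensity model, the outcome model and the key sensitivity analysis alike. The planned analyses neither remove the resulting bias nor reveal it.

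Its size cannot be taken from the document. Under the assumed effects and imbalances it is 0.5 to 12 points, in either direction, against the planned 15. It is zero if route and prior intubation are balanced given the seven factors. The range rests on a single binary factor, no true dose effect and a risk-difference scale. The change is worth making because the fields are already being gathered and the sample can absorb it.

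**What to change.** 1. Add two terms to the propensity model: route of first dose, coded as thin catheter against any endotracheal tube, and intubation at resuscitation before the first dose. Match exactly or stratify on both. Do not separate endotracheal tube from INSURE. State how the option for other routes is handled.
2. Include both terms in the outcome model, in the matched and unmatched analyses, where events and non-events occur at each level.
3. Report balance on both after matching.
4. Add a sensitivity analysis in infants not already mechanically ventilated before the first dose, since those already ventilated may meet the endpoint regardless of dose.
5. State what happens to infants without the rescue-only FiO2 field. Add prophylactic versus rescue setting only if they stay in the mITT.

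**Data limits to settle in the wording.** The rescue table has one route entry per day beside a count of that day's doses, so route of first dose needs a rule when several doses fall on one day. Appendix A records the respiratory support device per calendar day, so it cannot by itself order ventilation and surfactant on the same day. For delivery-room doses, the intubation code may be the same act as giving surfactant by tube.

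**Cost.** This is mainly wording, since the route and resuscitation fields are already planned. Some further infants will go unmatched, and because the mITT requires complete propensity factors, any with these fields missing would also drop out; the protocol gives no basis for estimating how many. If half of the smaller group is unmatched, about 227 to 292 pairs and 90 to 96% power remain.
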